11.1.1 Duration of Response

Duration of overall response: The duration of overall response is measured from the time measurement criteria are met for CR or PR or HI (for those with MDS) (whichever is first recorded) until the first date that recurrent or progressive disease is objectively documented.

The duration of overall CR is measured from the time measurement criteria are first met for CR until the first date that progressive disease is objectively documented.

Duration of stable disease: Stable disease is measured from the start of the treatment until the criteria for progression are met, taking as reference the smallest measurements recorded since the treatment started, including the baseline measurements.

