Additionally, efficacy of decitabine plus ipilimumab will be assessed for the total number of patients enrolled at the MTD/RP2D for each arm. Anti-leukemic activity will be described in terms of best overall response rate (for AML, to include CR+CRI; for MDS, to include CR+marrow CR+PR+HI). Assuming 6 patients are enrolled at the MTD/RP2D from the dose escalation phase and an additional 6 patients for the cohort expansion, the 90% exact binomial confidence interval will be within +/- 25%. Assuming 6 patients are enrolled at the MTD/RP2D from the dose escalation phase and an additional 12 patients from the cohort expansion, the 90% exact binomial confidence interval will be within +/- 21%.

Overall survival (OS) is defined as the time from registration to death due to any cause or censored at the date last known alive. Progression-free survival (PFS) is defined as the time from registration to the earlier of progression or death due to any cause. Survival outcomes will be

estimated by the method of Kaplan and Meier. OS and PFS will be evaluated within each arm.

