13.5 Analysis of Secondary Endpoints

Safety analyses will be based on the safety population, defined as all enrolled patients receiving at least 1 dose of ipilimumab. Categorical data will be presented as frequencies and percentages. All tests of treatment effects will be conducted at a 2-sided alpha level of 0.05, unless otherwise stated. All tests of interactions will be conducted at a 2-sided alpha level of 0.1, and all CIs will be given at a 2-sided 95% level, unless otherwise stated. Patients who are registered to the study and have received at least one dose of ipilimumab on study will be evaluable for response.

Clinical response to treatment will be assessed following the 2003 IWG criteria for AML [6] and the 2006 IWG criteria for MDS [7]. Anti-leukemic activity will be described in terms of best overall response rate (for AML, to include CR+CRi; for MDS, to include CR+marrow CR+PR+HI), PFS, OS, and remission duration. Time to event summaries will use the Kaplan-Meier method. We will separately evaluate the incidence of acute GVHD and chronic GVHD in patients in the post-allo-HCT cohort, and compare these events with response to treatment.

The focus of this trial is to establish the safety and RP2D of the combination; thus the biomarker studies should be considered exploratory. We will evaluate whether or not absolute lymphocyte count can predict for response for patients who receive combination treatment. ALC levels will be divided into: low (<1000 cells/ul) and normal/high (greater than or equal to 1000 cells/ul). We will compare the response and overall survival of patients with low ALC versus normal/high ALC using Kaplan-Meier estimates and differences will be assessed using log-rank test. We will further capture the absolute change in ALC level measured at baseline to end of cycle 2 (collected prior to dosing on cycle 3 day 1) for response and survival differences. For correlative laboratory tests, we will compare nonrandom measurements in an individual patient either across time (pre-treatment versus on-treatment) with a paired Student *t* test. OS will be censored at the date of last contacts.

REFERENCES

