APPENDIX D ACUTE MYELOID LEUKEMIA RESPONSE CRITERIA

Cheson, B et al., J Clin Oncol, 2003, 4642-9.

Morphological Complete Remission (CR):

-Normalization of the peripheral blood absolute neutrophil count $> 1.0 \times 10^9/L$, platelets $>$ than $100 \times 10^9/L$ no residual evidence of extramedullary disease and bone marrow aspirate with $\leq 5\%$ blasts, no blasts with Auer rods

Morphological Complete Remission with incomplete blood count recovery (CRi):

-Same as CR but without normalization of the peripheral blood absolute neutrophil and platelet count

Relapse from CR or CRi:

-Reappearance of leukemic blasts in the peripheral blood; or $> 5\%$ blasts in the bone marrow not attributable to another cause (e.g. recovery of normal cells following treatment-induced aplasia or use of growth factors) OR
-Appearance or reappearance of extramedullary disease.
-If there are no circulating blasts and no extramedullary disease and the bone marrow blast percentage is $> 5\%$ but $< 20\%$, then a repeat bone marrow performed at least 7 days after the first marrow examination and documenting bone marrow blast percentage $> 5\%$ is necessary to establish relapse.

Partial Remission (PR):

-Normalization of the peripheral blood absolute neutrophil count $1.0 \times 10^9/L$, platelets $>$ than $100 \times 10^9/L$, and at least a 50% decrease in the percentage of marrow aspirate blasts to 5-25%, or marrow blasts $< 5\%$ with Auer rods.

Cytogenetic Responses

Complete cytogenetic response: An abnormal clone is detected in all metaphases prior to treatment and only normal metaphases are observed in all metaphases following treatment.

Partial cytogenetic response: An abnormal clone is detected in all metaphases prior to treatment and the post-treatment sample has 50% or fewer abnormal metaphases compared to the pretreatment value.

Cytogenetic non-response: An abnormal clone is detected in all metaphases prior to treatment and neither complete nor partial cytogenetic response is observed in post-treatment specimens. Specimens with normal cytogenetic results before treatment will not be evaluated for cytogenetic response. The method used to determine cytogenetic response will be standard metaphase cytogenetics.

Stable disease:

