APPENDIX E MDS RESPONSE CRITERIA

Table below from IWG 2006 criteria (Cheson B, Blood, 2006, 419-425)

Category	Response criteria (responses must last at least 4 wk)
Complete remission	Bone marrow: $\leq 5\%$ myeloblasts with normal maturation of all cell lines* Persistent dysplasia will be noted*† Peripheral blood‡ Hgb ≥ 11 g/dL Platelets $\geq 100 \times 10^9/L$ Neutrophils $\geq 1.0 \times 10^9/L$ † Blasts 0%
Partial remission	All CR criteria if abnormal before treatment except: Bone marrow blasts decreased by $\geq 50\%$ over pretreatment but still $> 5\%$ Cellularity and morphology not relevant
Marrow CR†	Bone marrow: $\leq 5\%$ myeloblasts and decrease by $\geq 50\%$ over pretreatment† Peripheral blood: if HI responses, they will be noted in addition to marrow CR†
Stable disease	Failure to achieve at least PR, but no evidence of progression for > 8 wks
Failure	Death during treatment or disease progression characterized by worsening of cytopenias, increase in percentage of bone marrow blasts, or progression to a more advanced MDS FAB subtype than pretreatment
Relapse after CR or PR	At least 1 of the following: Return to pretreatment bone marrow blast percentage Decrement of $\geq 50\%$ from maximum remission/response levels in granulocytes or platelets Reduction in Hgb concentration by ≥ 1.5 g/dL or transfusion dependence
Cytogenetic response	Complete Disappearance of the chromosomal abnormality without appearance of new ones Partial At least 50% reduction of the chromosomal abnormality
Disease progression	For patients with: Less than 5% blasts: $\geq 50\%$ increase in blasts to $> 5\%$ blasts 5%-10% blasts: $\geq 50\%$ increase to $> 10\%$ blasts 10%-20% blasts: $\geq 50\%$ increase to $> 20\%$ blasts 20%-30% blasts: $\geq 50\%$ increase to $> 30\%$ blasts Any of the following: At least 50% decrement from maximum remission/response in granulocytes or platelets Reduction in Hgb by ≥ 2 g/dL Transfusion dependence

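### Duration rules in 11.1.1 omit CRi and marrow CR as starts and recurrence as an end of CR; read literally, an AML relapse below ELN PD is not a PFS event

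*Combined protocol and SAP*

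**What the plan says.** **Responses counted.** Section 13.1 describes activity by "best overall response rate (for AML, to include CR+CRI; for MDS, to include CR+marrow CR+PR+HI"). Section 13.5 repeats this and adds duration: "for MDS, to include CR+marrow CR+PR+HI), PFS, OS, and remission duration". Section 11.1 lists the same categories. CRi and marrow CR are categories of their own. Appendix D defines CRi as "Same as CR but without normalization of the peripheral blood absolute neutrophil and platelet count". Appendix E treats HI as an optional addition to marrow CR: "if HI responses, they will be noted in addition to marrow CR".

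**Duration rules.** In Section 11.1.1, overall response duration "is measured from the time measurement criteria are met for CR or PR or HI (for those with MDS"), whichever is recorded first, and runs "until the first date that recurrent or progressive disease is objectively documented". The next sentence runs CR duration from when criteria are "first met for CR until the first date that progressive disease is objectively documented".

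**PFS.** Sections 11.1.2 and 13.1 define the event as progression or death from any cause. Section 11.1.2 censors patients alive without progression at their last disease evaluation. Sections 5.5 and 11.1 assign AML progression to ELN 2017 (Appendix H), and Section 11.1 makes the screening marrow the baseline. Appendix H has separate entries for progressive disease and hematologic relapse. Appendix D also defines relapse and PD separately.

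**Objectives served.** Duration of remission (1.2.5) and PFS at 1 year (1.2.4), both secondary.

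**The concern.** The response rate and the duration of response should describe the same patients. Here some patients enter the rate but cannot enter the duration, and others who pass through CRi or marrow CR before CR start late. CR duration has a narrower stopping rule than overall response duration, with no reason given.

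For AML PFS, the difficulty is that ELN PD measures growth over the screening marrow. A patient who has cleared the marrow and relapses can be far below that level. If relapse is not itself an event, a living patient in that position is censored at the last evaluation, and one who dies becomes an event only at death. Both lengthen PFS. Two analysts could report different 1-year PFS and different durations from the same data.

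**Working it through.** No sample size, power or alpha in the plan depends on these definitions, so there is no stated figure to reproduce. The check compares the rules term by term and then finds where ELN PD begins.

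**1. Start rule**

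| Disease | Counted response | Start in 11.1.1 |
|---|---|---|
| AML | CR | yes |
| AML | CRi | not named |
| MDS | CR, PR, HI | yes |
| MDS | marrow CR | not named; dated only if HI, PR or CR is also met |

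AML PR is the reverse case. It is not counted in the rate, yet it may start a duration, depending on whether the bracketed MDS qualifier covers PR or only HI.

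**2. End rule.** Overall response ends at recurrence or progression; CR ends at progression only. An AML patient in CR whose disease recurs below PD has ended the overall response but not the CR.

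**3. Marrow level at which ELN PD is met.** Inputs: Appendix H (a rise of more than 50% over baseline, and at least 15 points if baseline is below 30%) and Section 11.1 (baseline is screening). For screening blasts B:

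- B < 30%: at least max(1.5B, B + 15)
- B ≥ 30%: more than 1.5B

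| Screening B | PD by marrow rise | Relapse (Appendix H) |
|---|---|---|
| 5% | max(7.5, 20) = 20% | ≥ 5% |
| 20% | max(30, 35) = 35% | ≥ 5% |
| 30% | > 45% | ≥ 5% |
| 40% | > 60% | ≥ 5% |
| 60% | > 90% | ≥ 5% |
| 67% | > 100.5%, unattainable | ≥ 5% |

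Example: screening 40%, CR, then 20%. This is a relapse and is not PD by marrow rise. Appendix H has three other PD routes: marrow blasts persistently above 70% over at least 3 months (without the specified count improvement), blood blasts rising more than 50% to above 25 × 10⁹/L, and new extramedullary disease. If none applies, no PFS event is recorded on the literal reading.

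**4. Are progression and relapse one term in this protocol?** Section 3.2.3 names progression and relapse as two things and then defines AML progression by ELN progressive disease, giving the rise over baseline as an example. Section 11.1 records best response until progression or recurrence, naming both. Section 11.1.2 names only progression.

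**5. MDS.** Appendix E progression includes a 50% fall from best granulocytes or platelets, a hemoglobin fall of 2 g/dL and transfusion dependence, so it captures most MDS relapses.

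**6. How common is an undated response?** Section 2.1 cites a decitabine MDS study with 17 CR, 15 marrow CR and 18 hematologic improvements: 17 + 15 + 18 = 50, and 15/50 = 30%. This is an upper figure, because a marrow CR with HI could be dated at HI. The documents give no CRi rate.

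**The case against.** The strongest reply is that Section 11.1 invokes the ELN 2017 criteria through Appendix H as a whole, and that table contains the relapse entry. A sensible analyst might therefore count relapse. That reading is possible, and it limits the PFS part to what follows from the literal text. It does not settle the matter: no section says that relapse counts as progression, and Sections 3.2.3 and 11.1 name the two separately.

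A second reply is that Section 11.1.1 supplies a nadir reference, "taking as reference the smallest measurements recorded since the treatment started, including the baseline measurements". That clause concerns stable disease. If it were borrowed for PFS, with both ELN rules run from a nadir of 0% to 5%, PD would begin at 15% to 20%. The 20% example would then be an event, but relapses from 5% up to that level would still be missed.

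Third, Section 13.1 evaluates PFS within each arm, pooling AML and MDS, which dilutes the effect. That stands.

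Some stronger inferences are tempting and not supported:

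- **Follow-up after removal is by phone only.** Besides the quarterly calls, Section 10.1 asks for a clinical exam about 3 months after last treatment and lists an end-of-study marrow. Section 6.2 follows patients stopped for GVHD for response for up to 1 year.
- **The marrow interval is the bias.** Scheduled marrows are 8 weeks apart (cycle 2 to 4) or 12 weeks apart (4 to 7, 7 to 10), but nothing shows that the next marrow would meet PD, and clinical concern triggers earlier ones.
- **The small number of responders sizes the start-date gap.** Few responders give each one a large weight, but that does not show how many lack a start date.
- **The Appendix D PD paragraph is redundant.** Appendix D defines stable disease by reference to it, and Section 5.1 uses stable disease to decide entry to maintenance.

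**Conclusion.** The two duration defects are on the face of the text. CRi and marrow CR are counted without being start points, and CR duration omits the recurrence that ends overall response. The PFS defect holds on the literal reading, which the rest of the protocol favors without stating it outright.

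The PFS effect is confined to AML patients who reach CR or CRi and then relapse without meeting any ELN PD route. For them the direction is clear: PFS is lengthened, and so is CR duration where CR was reached. The amount cannot be computed from the documents. For the start-date gap, the only documented guide is the 30% upper figure for marrow CR in MDS.

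Unaffected are overall response duration at its end point, deaths in PFS, most MDS relapses and the MTD/RP2D. The endpoints concerned are secondary and descriptive. The correction should still be made before analysis, because followed as written the rules drop or misdate counted responders.

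**What to change.** - **11.1.1, start:** begin response duration at the first response counted in the rate (AML: CR or CRi; MDS: CR, marrow CR, PR or HI).
- **11.1.1, end:** end CR duration at recurrence or progression, as overall response duration already does.
- **11.1.2 and 13.1:** count relapse after CR/CRi as an AML PFS event alongside progression and death, dated at first documentation and based on assessments already made.
- **Name one relapse definition for the analysis.** With no circulating blasts or extramedullary disease, Appendix D requires a repeat marrow at least 7 days later when blasts are above 5% but below 20%. Appendix H takes 5% or more without confirmation. The calendar schedules no confirmatory marrow, so if Appendix D is chosen, say how an unconfirmed low-level relapse is handled.
- **Appendices D and H:** keep the Appendix D PD paragraph. State that the two PD definitions differ (best assessment with a floor, against screening baseline) and must be reconciled.

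These are changes to endpoint definitions only; the rules for stopping or continuing treatment are untouched. The cost is wording, with no added visits. AML CR duration and PFS will come out somewhat shorter, and relapses after removal from study may still be incompletely captured.

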1.2 Secondary Objectives

- 1.2.1 To observe and record anti-tumor activity. Although the clinical benefit of this novel combination has not yet been established, the intent of offering this treatment is to provide a possible therapeutic benefit, and thus the patient will be carefully monitored for tumor response and symptom relief in addition to safety and tolerability.

- 1.2.2 To determine the overall response rate (ORR) including complete remission (CR) and complete remission with incomplete count recovery (CRi) for AML following 2003 IWG response criteria [6].
- 1.2.3 To determine the ORR including CR, partial remission, marrow CR, hematologic improvement for MDS using 2006 IWG criteria [7].
- 1.2.4 To determine the overall survival and progression free survival at 1 year.
- 1.2.5 To determine the duration of remission.
- 1.2.6 To capture the incidence and severity of acute graft-versus-host disease (GVHD) in the post allo-HCT cohort.
- 1.2.7 To capture the incidence and severity of chronic graft-versus-host disease (GVHD) in the post allo-HCT Cohort

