11.1.2 Progression-Free Survival

Overall Survival: Overall Survival (OS) is defined as the time from time of registration to death due to any cause, or censored at date last known alive. We will evaluate for survival differences among patients that respond based on transplant status.

Progression-Free Survival: Progression-Free Survival (PFS) is defined as the time from time of registration to the earlier of progression or death due to any cause. Participants alive without disease progression are censored at date of last disease evaluation.

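### Neither response duration nor CR duration ends at death, and with Kaplan-Meier as the only stated method, responders who die in remission would by default be censored

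*Combined protocol and SAP*

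**What the plan says.** Remission duration is a named secondary objective (section 1.2: "To determine the duration of remission"). Section 13.5 lists it among the measures of anti-leukemic activity ("PFS, OS, and remission duration") and adds: "Time to event summaries will use the Kaplan-Meier method". No cumulative-incidence or other competing-risk method appears.

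Section 11.1.1 defines two durations:

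- Overall response runs from the first qualifying response "until the first date that recurrent or progressive disease is objectively documented".
- CR runs from the first CR "until the first date that progressive disease is objectively documented". Recurrence is not named here, although Appendices D, E and H each define relapse separately.

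Neither definition mentions death and neither has a censoring rule. Section 11.1.2 has both for PFS: the event is "the earlier of progression or death due to any cause", and "Participants alive without disease progression are censored at date of last disease evaluation". The MDS table in Appendix E does mention death, in its failure category ("Death during treatment or disease progression characterized by worsening of cytopenias"), but the duration definitions do not use that category.

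**The concern.** Kaplan-Meier recognises only events and censored times. If death is not an event, a responder who dies in remission leaves the risk set as censored, and the curve is computed as though that patient could still have stayed in remission. The same patient has a PFS event and an open-ended remission. The reader of a remission-duration curve usually wants to know how many responders are still alive and in remission, and this curve would not show that.

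Durability matters here because section 2.4 rests part of its rationale on long-lasting responses, and section 1 makes a future phase 2 trial depend on preliminary efficacy as well as safety. Death without relapse is plausible: section 2.2 describes fatal immune-mediated reactions to ipilimumab.

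The CR wording adds a second gap. Under Appendix H, haematologic relapse needs marrow blasts of 5% or more. Progression by marrow blasts needs a rise of more than half over baseline, and of at least 15 points where baseline was below 30%. A patient can therefore relapse from CR without meeting that progression criterion, and read literally the CR duration would continue.

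**Working it through.** The plan states no figure for remission duration, its expected number of events or its precision, so there is nothing of its own to reproduce.

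**Direction.** Suppose deaths are censored on the date of death. The risk sets are then the same whether or not death counts as an event. Counting it multiplies the estimate by an extra factor (1 − d/n) ≤ 1 at each death time. The curve with deaths censored therefore lies at or above the other, and the two coincide only if no responder dies in remission. Censoring at the last disease evaluation before death can disturb this ordering in a single small sample, but deaths are still left out of the event count.

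A made-up example with six responders: deaths in remission at months 2 and 5, relapses at months 4, 8 and 11, one ongoing at month 14.

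- Deaths censored, month 8: 4/5 × 2/3 = 53%.
- Deaths counted, month 8: 5/6 × 4/5 × 3/4 × 2/3 = 33%.

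**Size, on assumed inputs.**

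- Median time to relapse or progression, m: 9 or 14 months. Section 2.3 quotes 9–14 months as the median response duration on single-agent decitabine. It is used here only for scale.
- Net 12-month risk of death in remission, q: 10%, 20% or 30%. This is an assumption; the documents give no value. Net means the risk if relapse did not intervene.
- Constant, independent hazards: relapse λr = ln 2 / m; death λd = −ln(1 − q) / 12.

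Formulas:

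- 12-month Kaplan-Meier estimate with deaths censored = exp(−12 λr) = 2^(−12/m).
- Alive in remission at 12 months = exp(−12(λr + λd)) = 2^(−12/m) × (1 − q).
- Excess = 2^(−12/m) × q.
- Median with deaths censored = m; median with death as an event = ln 2 / (λr + λd).

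| m (months) | q | Deaths censored, 12 mo | Alive in remission, 12 mo | Excess (points) | Median, death as event (months) |
|---|---|---|---|---|---|
| 9 | 10% | 39.7% | 35.7% | 4 | 8.1 |
| 9 | 20% | 39.7% | 31.7% | 8 | 7.2 |
| 9 | 30% | 39.7% | 27.8% | 12 | 6.5 |
| 14 | 10% | 55.2% | 49.7% | 6 | 11.9 |
| 14 | 20% | 55.2% | 44.2% | 11 | 10.2 |
| 14 | 30% | 55.2% | 38.6% | 17 | 8.7 |

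Because q is a net risk, fewer patients than q actually die in remission by month 12: λd/(λr + λd) × (1 − alive in remission). At q = 30% this is about 20% (m = 9) or 23% (m = 14).

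**Second parametrisation.** If s is the share of first events that are deaths, the median is inflated by the factor 1/(1 − s). For s = 10%, 20%, 30% and 40% the overstatement is 11%, 25%, 43% and 67%. At s = 0 it is nil.

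**The case against.** The strongest reply is that the plan never says deaths in remission are censored. That is correct: it is the default consequence of the definition in section 11.1.1 combined with the method in section 13.5. The plan also relies on published response criteria that the appendices reproduce only in part, and whether those criteria set a rule for death cannot be seen from these documents. The point is therefore worded as a default, but nothing in the documents replaces that default.

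A reader might infer that the bias is largest in the post-transplant arm. The documents do not support this. Section 2.4 raises a GVHD concern at higher doses but gives no non-relapse mortality for either arm. Prior grade III–IV acute GVHD is excluded, and each arm finds its own MTD. In the earlier post-transplant ipilimumab study, one patient with colitis and pneumonitis died, with remission status not stated. Untreated AML is eligible only at age 75 or older, a group that may also die without relapse.

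A reader might also fear a misleading comparison of remission duration between arms. None is planned. Section 11.1.2 plans a comparison by transplant status among responders, but of survival, which counts every death.

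On size, the objection largely stands. The 9–14 months come from studies of older, untreated AML, and how those studies handled death is not visible; if they counted it, using their medians as a pure relapse process counts it twice. Under independent hazards, Kaplan-Meier validly estimates a net relapse-free probability. The overstatement is therefore relative to being alive in remission, which is a different quantity. Sampling error will also be large: with 24 patients in an arm and an assumed 30% response rate there are about 7 responders, and the exact 95% interval for 3 of 7 is roughly 10% to 82%. That limits the consequence, but imprecision does not justify a definition that pushes the estimate one way.

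**Conclusion.** The point holds as a gap in the endpoint definition with a predictable direction. Applied as written, section 11.1.1 gives a responder who dies in remission no duration event, and the Kaplan-Meier summary then presents too favourable a picture of time alive in remission. The CR definition has the further gap that relapse is not an end event.

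The size is illustrative. The excess of about 4 to 17 points at 12 months rests on assumed relapse medians of 9–14 months, an assumed 10–30% net risk of death in remission, and constant independent hazards. It is zero if no responder dies in remission. The effect may differ between arms, in a direction the documents do not settle.

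This is a descriptive secondary endpoint of a phase 1 study. MTD/RP2D, OS and PFS are unaffected. It should still be corrected, because the remedy is short and is best fixed before the data are seen.

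**What to change.** In section 11.1.1, end both duration of response and duration of CR at the earliest of relapse or recurrence, progression, or death from any cause. Censor patients alive without relapse or progression at their last disease evaluation, as is already done for PFS.

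Alternatively, keep relapse or progression as the event, naming relapse for CR as well, and in section 13.5 report its cumulative incidence with death in remission as a competing event.

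Under either option, report by arm the number of responders who die in remission.

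The cost is a sentence or two. No new data are needed, because section 5.6 already follows patients until death or up to one year after removal from study. The downside is that reported durations become somewhat shorter if death is made an event.
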